4.0 Test Schedule

Assessments, tests and procedures	Treatment			Observation ⁷
	Baseline ²	Last day of treatment (+/- 2 days)	12 weeks (+/- 8 weeks) post-radiation	12 months (+/- 3 month) post completion of radiotherapy, 24 months (+/- 3 months), 36 months (+/- 3 months), and at 5 years (+/- 3 months)
History and Physical exam (including breast assessment/exam) ¹	X	X	X	X
Mammogram	X ¹⁰			X ¹¹
Cosmesis ,QOL Outcome Assessment and Breast-Q ¹⁶ (see section 11.3 and Appendix)	X ¹³	X	X	X
Digital Photograph	X	X	X	X
Review of surgical specimen(s) to confirm eligibility	X ³			
Echocardiography ^{9, 14}	X ¹³			X ⁸
Radiation toxicity assessment (see section 10.4)	X	X	X	X
Serum pregnancy test	X ⁴			
Blood specimen ^{5, 17, R}	X ¹⁵	X	X	X ¹²
Surgical tumor specimen ^{6, 18, R}	X			

1. A general history & physical must be done \leq 8 weeks prior to registration. This should include an assessment of ECOG performance status (see Appendix I).

2. Following definitive surgical resection and adjuvant chemotherapy if indicated, prior to the start of radiation.
3. Outside pathology must be reviewed at the treating institution.
4. For women of childbearing potential only, must be within 7 days of radiotherapy
5. See section 14 for collection time and preparation of samples
6. See section 17 for collection time and preparation of samples
7. Patients that cannot come back to Mayo Rochester within the time constraints of the follow-up schedule; efforts to obtain outside records and send QOL's to be completed will occur, however the required items may not be captured.
8. Ideally 6-12 months post radiotherapy in HER2 positive patients treated with HER2 directed therapy and in patients treated with anthracycline as part of routine clinical care. Only followed for Echos 1 year post therapy.
9. Co-enrollment on IRB 15-007443 (echo protocol) is required in Rochester while open
10. Completed \leq 12 months prior to study entry
11. As clinically indicated
12. At 12 months post-treatment visit only to coincide with echocardiography.
13. Should be \geq 14 days since last chemotherapy
14. After closure of IRB 15-007443 (echo protocol) echocardiography tests will be performed only in left sided patients previously treated with anthracycline and/or HER2 directed systemic therapy. This correlative component will occur at Rochester Mayo only.
15. Baseline blood collection will be drawn through co-enrollment on IRB 15-000136 (Radiation Oncology Outcomes Registry and Biobanking Study).

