16. Breast-Q forms to be completed by patient at Observation timepoints.
17. Post radiation blood specimen submission for Rochester site only.
18. Surgical tumor specimen for Rochester site only.

R. Research funded

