5.0 Randomization Factors

5.1 Assignment of treatments will be balanced with respect to the presence of immediate reconstruction (mastectomy/immediate reconstruction vs mastectomy/no immediate reconstruction) using a biased-coin minimization algorithm.[29]

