16.4 Sample Size Determination

The proposed trial design is a randomized phase II trial with a 1:1 randomization ratio with the stratification variable noted in section 5.1. The primary endpoint for this trial is the 24-month complication rate, as defined above. The study will plan to enroll a total of 72 evaluable patients. An evaluable patient is defined as a patient who receives any dose of the protocol-defined radiotherapy. In this trial, we will accrue and randomize up to 96 patients over 3 years to account for ineligibility, cancellations (withdrawals prior to protocol therapy), major treatment violations, or other reasons, and treat a total of 82 patients in order to ensure 72 evaluable patients at 24 months.

This study is designed as a non-inferiority/superiority “hybrid” design using the approach of Freidlin et al.[36] It is estimated that approximately 2/3 of the patients will undergo reconstruction. For patients who undergo mastectomy with immediate reconstruction, the rate of unplanned surgical complications at the Mayo Clinic is ~15% (personal communications with [name] and [name] 6/2014), comparable to what has been reported in the literature in the modern era.[27]. The rate of grade 3 or greater late toxicity in this population is expected to be $\leq 1\%$ (Whelan ASCO 2011). For the purpose of designing this trial, we will assume a 10% complication rate in the control arm. We consider that a 10% increase of this rate in the experimental arm would be acceptable (i.e. a non-inferiority margin of 10%). Based on the results of the START-B clinical trial[9], it is also plausible that toxicities in the experimental arm may even be reduced with the shortened fractionation schedule. Therefore, a marginal *decrease* in complication rate in the experimental arm to 5% (i.e. marginal benefit margin of 5%) may be reasonably expected. Denote p_0 and p_1 as the 24-month complication rate in the control arm and experimental arm, respectively. The null hypothesis is that the complication rate in the experimental arm is inferior to the control rate of 10% by more than 10% (i.e. $H_0: p_1 - p_0 > 10\%$). The alternative hypothesis is that the complication rate in the experimental arm is non-inferior to the control rate of 10% (i.e. $H_A: p_1 - p_0 < 10\%$).

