16.62 Secondary Analyses

16.621 *Acute adverse events (up to 90 days post-RT):* All patients who were registered to the study and started treatment will be included in the acute adverse event analysis. An acute adverse event is an AE, regardless of attribution, that occurs up to 90 days post-RT. The maximum grade for each type of acute AE will be recorded for each patient. Data will be summarized as frequencies and relative frequencies by treatment arm. Additionally, the relationship of the adverse event(s) to the study treatment will be taken into consideration.

16.622 *Late adverse events and reconstruction failure:* All patients who were registered to the study and started treatment will be included in the late adverse event and reconstruction failure analysis. A late adverse event is an AE, regardless of attribution, that occurs at least 90 days post-RT and up to 5 years post-RT. The maximum grade for each type of late AE will be recorded for each patient. Data will be summarized as frequencies and

relative frequencies by treatment arm. Additionally, the relationship of the adverse event(s) to the study treatment will be taken into consideration.

- 16.623 *Quality of life*: The subscales of the BCTOS, elements from CTCAE-PRO, and other patient reported measures such as fatigue, breast pain, breast shape, and arm related morbidity outlined in the appendix will be summarized as the mean \pm SD and median (minimum value, maximum value). Changes in the QOL measurements from baseline will be determined at each follow-up visit and measured by treatment arm. The comparison of the changes at each time point between the two treatment arms within each cohort will be done with a paired t-test or Wilcoxon signed rank test, whichever is appropriate.
- 16.624 *Cosmesis*: The values of the cosmesis instruments (patient self-reported and panel-assessed) will be summarized with the frequencies and confidence intervals of fair or poor cosmesis events at baseline, 2 years, and 5 years by treatment arm.
- 16.625 *IBTR incidence*: The IBTR cumulative incidence will be estimated using a competing risks method (Gooley et al.) by treatment arm. The competing risks will be regional/distant breast cancer recurrence and death.

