- 16.626 *Regional recurrence incidence*: The regional breast cancer recurrence cumulative incidence will be estimated using a competing risks method (Gooley et al.) by treatment arm. The competing risks will be local/distant breast cancer recurrence and death.
- 16.627 *Distant recurrence incidence*: The distant breast cancer recurrence cumulative incidence will be estimated using a competing risks method (Gooley et al.) by treatment arm. The competing risks will be local/regional breast cancer recurrence and death.
- 16.628 *Disease-free survival*: DFS is defined as the time from registration until the time of disease recurrence or death due to any cause. The DFS will be estimated with a Kaplan-Meier estimator and curve by treatment arm. Estimates will be given for specific time points along with 95% CIs.
- 16.629 *Overall survival*: The OS will be estimated with a Kaplan-Meier estimator and curve by treatment arm. Estimates will be given for specific time points along with 95% CIs.
- 16.63 Exploratory Analyses: 2D and 3D strain parameters will be analyzed after radiotherapy compared to baseline and will be compared between patients undergoing conventional versus hypoofractionated radiotherapy. Continuous variable will be compared using unpaired t tests and nominal variables will be compared using contingency tables and Chi square analyses.
- 16.64 Correlative Analyses:

16.641 Cardiac toxicity

Cardiac toxicity remains an important late effect of radiotherapy for breast cancer.[3, 34, 37, 38] Echocardiography is a noninvasive tool that enables the detection of cardiovascular disease as a result of radiotherapy. Echocardiography can detect pericardial disease, left ventricular systolic and diastolic dysfunction, coronary artery disease suggested by resting or stress-induced regional wall motion abnormalities, and valvular heart disease.[33] Ideally, cardiac toxicity could be predicted prior to the onset of clinical symptoms to enable an earlier opportunity for risk stratification, surveillance, and preventative interventions that reduce risk. Echocardiographic strain rate imaging, a measure of regional myocardial function, has previously been reported to detect subclinical decline in cardiac function in the anterior wall of patients treated with radiotherapy for left-sided breast cancer.[34]

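### Section 16.623 names paired tests for comparing quality-of-life change between two independent randomized arms

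*Combined protocol and SAP*

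**What the plan says.** Section 16.623 (Quality of life) covers the BCTOS subscales, PRO-CTCAE elements and other patient-reported measures. It first forms change scores: "Changes in the QOL measurements from baseline will be determined at each follow-up visit and measured by treatment arm". It then says that the comparison of these changes at each time point "between the two treatment arms within each cohort will be done with a paired t-test or Wilcoxon signed rank test", choosing whichever of the two suits the data.

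The design is a parallel-group one. Section 16.4: "The proposed trial design is a randomized phase II trial with a 1:1 randomization ratio". Section 5.1: "Assignment of treatments will be balanced with respect to the presence of immediate reconstruction", and this is done "using a biased-coin minimization algorithm". No section sets up matched pairs across arms, and none defines a cohort.

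For the echocardiographic strain parameters, compared between the same two fractionation arms, section 16.63 says: "Continuous variable will be compared using unpaired t tests".

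**The concern.** A paired t-test and a Wilcoxon signed-rank test both work on within-pair differences. Here the only natural pair is a patient's own baseline and follow-up score, and that pairing is already used up in forming the change score. What remains is two independent sets of changes, for which neither test is defined. The freedom to choose the more suitable test does not help, because both candidates are paired.

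An analyst following the sentence has three options, all unsatisfactory:
- pair patients across arms arbitrarily;
- drop patients until the numbers match;
- run the test within each arm, which answers a different question (did scores change over time?) and leaves the announced arm comparison without a test.

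Patient-reported outcomes are a stated secondary goal (2.24). The trial is open label and these outcomes are subjective, so the test should be fixed before data are seen and not repaired afterwards.

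**Working it through.** The plan gives no alpha, effect size, SD or power for the quality-of-life comparison, so there is no figure of its own to reproduce. The checks below measure what the named tests would do.

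**Inputs.** 72 evaluable patients at 1:1 (16.4) give 36 per arm. Two-sided alpha of 0.05, completion rates, SD and effect sizes are assumptions.

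**1. Can the arms be paired one to one?** If each patient completes a visit independently with probability c, the number completing in each arm is Binomial(36, c). The probability of equal numbers is the sum over k of [P(X = k)]².

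| Completion c | P(equal numbers) | P(unequal) |
|---|---|---|
| 70% | 0.102 | 0.898 |
| 80% | 0.118 | 0.882 |
| 90% | 0.158 | 0.842 |
| 95% | 0.223 | 0.777 |

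So at about 78% to 90% of visits no one-to-one pairing exists unless patients are dropped. In simulations at a 0.5 SD difference, dropping the unmatched patients gave 46.8% power against 51.3% for the unpaired test (36 vs 30 patients), and 48.7% against 54.2% (40 vs 32).

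**2. Equal numbers, random pairing: average behaviour.** In 20,000 simulated trials with independent normal changes and 36 per arm, the rejection rate with no difference was 4.9% for both tests. At 0.5 SD it was 53.8% (paired) against 55.4% (unpaired). Average error is therefore not the problem.

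**3. Equal numbers: dependence on the pairing.** With equal SDs, the two statistics are related by

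t(paired) = t(two-sample) / √(1 − r),

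where r is the sample correlation that the chosen pairing happens to produce. The degrees of freedom are 35 and not 70.

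- A difference of 0.47 SD gives t = 0.47 / √(2/36) = 1.994, two-sample p = 0.050.
- Under random pairing, r has mean 0 and SD 1/√35 = 0.169, so its central 95% is about ±0.33.
- r = +0.33: t = 1.994/√0.67 = 2.44, p = 0.020.
- r = −0.33: t = 1.994/√1.33 = 1.73, p = 0.093.
- The 35-df critical value is 2.030, so p < 0.05 needs r > 1 − (1.994/2.030)² = 0.035, which has probability of about 42%.

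Direct re-pairing of one simulated dataset agrees: over 10,000 pairings the central 95% of paired-t p-values was 0.021 to 0.093, with 41.7% below 0.05. The signed-rank p ran from 0.012 to 0.098 (2,000 pairings), against a single rank-sum p of 0.021.

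**4. If the test is run within each arm.** Suppose both arms shift equally, with no arm difference. The paired t has noncentrality (shift in SD) × √36 and 35 df. Shifts of 0.2, 0.3 and 0.5 SD of the change score give noncentralities of 1.2, 1.8 and 3.0, and rejection in each arm 21%, 42% and 83% of the time.

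**The case against.** The strongest case on the other side is that this is a wording slip with little practical effect. These are secondary comparisons with no stated alpha, power or decision rule, and 16.63 shows that the authors know the arms are unpaired. Several of the illustrations can also be challenged:

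- **The re-pairing example sits on the boundary.** It starts from a two-sample p of 0.050, where the decision flips most easily. With a two-sample p of 0.207, 0% of pairings fall below 0.05; at 0.094, 4%; at 0.0225, 98%; at 0.006, 100%. This stands. The p-value always depends on the pairing, but the significance decision is unstable only near the threshold.
- **The within-arm percentages are not error rates.** They are power to detect a real change over time. This also stands. They mislead only if significance in one arm and not the other is read as an arm difference.
- **The 78% to 90% range rests on assumed completion and on 36 per arm.** Section 16.4 plans to treat 82 patients, and 16.623 names no analysis population. If *cohort* meant reconstruction groups (about 24 and 12 per arm at the planned 2/3 to 1/3 split), equal numbers would occur in 13% to 28% and 18% to 42% of cases. Unequal numbers remain the more likely outcome throughout.
- **Footnote 7 of section 4.0 is limited support for missing data.** It says "however the required items may not be captured", but only for patients who cannot return to Rochester in time, only in the observation columns, and alongside a commitment to try to send the questionnaires. It shows that gaps are foreseen at 12 months and later, not at every visit.
- ***Cohort* may be left over from a wider design.** Sections 7.2 and 7.82 still mention lumpectomy, and the IBTR definition refers to breast parenchyma. This is an inference, but it favours deleting the word over inventing subgroups.

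None of this supplies a pairing across arms, and no other section corrects the sentence.

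**Conclusion.** The concern holds. Section 16.623 specifies tests that do not apply to the comparison it describes, and it conflicts with 16.63 for the same two arms. Followed literally, it gives a between-arm test that cannot be run without dropping patients at most visits (about 78% to 90%, under independent completion of 70% to 95% and 36 per arm), or one whose p-value depends on an arbitrary ordering of patients.

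The scope is narrow. Only the between-arm p-values for the 16.623 outcomes are affected. The primary endpoint, the sample size, the 16.623 descriptive summaries and the 16.624 cosmesis summaries are untouched. With equal numbers and random pairing, type I error stays nominal and the power loss is between one and two points. It should be corrected because the error is clear and the correction is nearly free.

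**What to change.** Replace the sentence in 16.623 with wording such as: *Changes from baseline at each time point will be compared between arms with a two-sample t-test or Wilcoxon rank-sum test, whichever is appropriate.* This matches 16.63. Keep paired tests only for change within an arm, if that is wanted, and say so. Delete the reference to cohorts, or define it; defining it by reconstruction would add small subgroup comparisons that the trial is not sized for.

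Optionally, where a baseline score exists, use ANCOVA of the follow-up score on arm, baseline score and immediate reconstruction. If so, confirm first which instruments have a baseline: footnote 16 of section 4.0 has "Breast-Q forms to be completed by patient at Observation timepoints", although the schedule row that includes Breast-Q is also marked at baseline.

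The cost is one sentence of analysis-plan text, with no change to data collection, visits or sample size.

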Preexisting Condition- A preexisting condition is one that is present at the start of the study. A preexisting condition should be recorded as an adverse event if the frequency, intensity, or the character of the condition worsens during the study period. At screening, any clinically significant abnormality should be recorded as a preexisting condition. At

the end of the study, any new clinically significant findings/abnormalities that meet the definition of an adverse event must also be recorded and documented as an adverse event.

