The investigator will review all adverse event reports to determine if specific reports need to be made to the IRB and FDA. The investigator will sign and date the adverse event report when it is reviewed. For this protocol, only directly related SAEs/UPIRTSOs will be reported to the IRB.

10.4 Adverse events to be graded at each evaluation and pretreatment symptoms/conditions to be evaluated at baseline per the CTCAE v4.0 grading unless otherwise stated in the table below:

System Organ Class (SOC)	Adverse event/Symptoms	Baseline	Each evaluation	Grading scale (if not CTCAE)
Skin and Subcutaneous tissue disorders	Dermatitis Radiation	X	X	CTCAE
	Telangiectasia	X	X	See 10.41

	Breast Edema = CTCAE Vascular Lymphedema	X	X	CTCAE, BCTOS ¹
	Superficial soft tissue Fibrosis	X	X	CTCAE
	Seroma Formation	X	X	CTCAE
	Skin hyperpigmentation	X	X	CTCAE
	Skin hypopigmentation	X	X	CTCAE
Gastrointestinal Disorders	Esophagitis	X	X	
Infections and infestations	Breast infection	X	X	CTCAE
Respiratory, thoracic and mediastinal disorders	Pneumonitis	X	X	CTCAE
General disorders and administration site conditions	Non-cardiac chest pain	X	X	CTCAE

1. BCTOS = Breast Cancer Treatment Outcomes Scale

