16.0 Statistical Considerations and Methodology

This is an open label phase II randomized controlled trial to determine the safety of 15 fraction vs 25 fraction scanning beam proton radiotherapy after mastectomy in patients requiring regional nodal irradiation.

16.1 Primary Endpoint:

16.1.2 Primary endpoint: 24 month complicate rate, defined as the percentage of women randomized who develop one or more of the following events:

- 1) grade 3 or higher late adverse events
- 2) unplanned surgical intervention (not including planned serial fat grafting) in patients who undergo mastectomy with reconstruction.

16.2 Secondary Study Endpoints: The secondary aims of this study are to characterize acute and late adverse events including grade ≥ 2 pneumonitis and reconstruction failure rate, assess patient self-reported cosmesis, evaluate fatigue, breast pain, arm function and other patient reported outcomes, compare the locoregional control, disease free, overall survival. Blood will be collected for future studies exploring dose volume and genomic predictors of adverse cosmesis and biomarkers of cardiotoxicity.

The following definitions are used for the secondary endpoints of interest:

- *Acute adverse events* (up to 90 days post-RT): any adverse event, regardless of attribution, that occurs in the first 90 days post-RT.
- *Late adverse events* (up to 5 years post XRT): any adverse event that occurred after the first 90 days post-RT and up to 5 years post-RT.
- *Reconstruction failure* (up to 5 years post XRT): loss of the tissue expander or implant with the inability to replace it resulting in no final reconstruction or conversion to autologous reconstruction or revised with the addition of autologous reconstruction.[27, 28]
- *Patient Reported Outcomes/Quality of life*: Elements of the Patient-Reported Outcomes Version of the Common Terminology Criteria for Adverse Events (PRO-CTCAE) will be used for patient self-reporting of toxicities. The Breast Cancer Treatment Outcomes Scale (BCTOS) will be used to measure patient reported functional status (pain, mobility). Other measures of fatigue, pain, and arm function are listed in the appendix.
- *Patient self-reported cosmetic outcomes*: the patient self-reported outcome will be assessed using a modified Harvard Cosmesis Scale and a modified BCTOS at baseline, 2 years, and 5 years.

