- *Panel assessed cosmetic outcome*: in addition to patient self-reported and physician reported outcomes, cosmesis will be assessed by a panel of breast cancer medical providers using digital photographs from baseline and at 2 years. The Panel will be blinded to treatment allocation.

- *IBTR*: this is defined as local recurrence from trial registration as a first event at 5 years. IBTR is defined as both invasive and non-invasive breast cancer involving the same breast parenchyma as the original tumor.
- *Regional recurrence*: invasive breast cancer in the axilla, regional lymph nodes, chest wall, and skin of the ipsilateral breast at 5 years.
- *Distant recurrence*: metastatic cancer that has either been biopsy confirmed or clinically diagnosed as recurrent invasive breast cancer at 5 years.
- *Invasive disease free survival*: this is defined as the time from study registration until the occurrence of one of the events in a composite endpoint. This endpoint includes invasive IBTR, regional invasive breast cancer recurrence, distant breast cancer recurrence, death due to any cause, contralateral invasive breast cancer, and second primary non-breast invasive disease.
- *Overall survival*: is defined as the time from registration to death due to any cause.

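### 16.624 does not use each woman's pre-radiotherapy cosmesis rating, so the 2-year arm comparison is unbiased but less precise and harder to interpret than the collected data allow

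*Combined protocol and SAP*

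**What the plan says.** **When baseline is taken.** Note 2 to the test schedule (4.0) places it "Following definitive surgical resection and adjuvant chemotherapy if indicated, prior to the start of radiation". Cosmesis, photographs and toxicity are all scheduled at that point.

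**Cosmesis ratings.** Under 16.2, "the patient self-reported outcome will be assessed using a modified Harvard Cosmesis Scale and a modified BCTOS at baseline, 2 years, and 5 years". The blinded panel rates cosmesis "using digital photographs from baseline and at 2 years".

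**Cosmesis analysis.** For the patient-rated and panel instruments, 16.624 gives "frequencies and confidence intervals of fair or poor cosmesis events at baseline, 2 years, and 5 years by treatment arm". It names no within-patient change, no adjustment for baseline and no between-arm difference.

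**Toxicity.** Section 10.4 reads: "Adverse events to be graded at each evaluation and pretreatment symptoms/conditions to be evaluated at baseline per the CTCAE v4.0 grading". Under 16.622, "The maximum grade for each type of late AE will be recorded for each patient", and 16.621 does the same for acute events. Neither mentions the baseline grade. Section 10.1 has a rule for conditions present at entry: "A preexisting condition should be recorded as an adverse event if the frequency, intensity, or the character of the condition worsens during the study period".

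**Elsewhere in 16.62.** Section 16.623 analyses the BCTOS subscales and other patient-reported measures as change from baseline.

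**The concern.** Every woman has had a mastectomy, and 16.4 expects about two thirds to have reconstruction. Some will therefore be rated fair or poor before the first fraction. Under 16.624, a woman rated poor at baseline and unchanged at 2 years counts in the 2-year frequency exactly like a woman who fell from good to poor after radiotherapy. Two marginal frequencies cannot show how many women worsened and how many improved.

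Three things are at stake: how each arm's 2-year rate is read, how far a chance baseline difference at about 36 per arm colours the comparison, and how wide the interval is around any arm difference a reader draws from the table. The strongest predictor of the later rating is probably the earlier one. It is collected and not used.

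The toxicity sections have a smaller, related gap. The 10.4 items are graded at baseline and at every evaluation, but 16.621 and 16.622 do not say how the baseline grade enters the maximum. Two analysts could build different tables from the same data.

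**Working it through.** **Inputs from the documents.** 1:1 allocation and 72 evaluable patients at 24 months, so 36 per arm (16.4). A four-level cosmesis scale (11.3.3), taken here to apply to the patient and panel ratings too.

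**Assumed, because the documents give no figure.** The fair/poor rate p (20% to 40%) and the baseline-to-2-year correlation. The correlation is stated on a latent normal scale unless called binary.

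**1. The plan's own figure.** There is none for cosmesis. The primary-endpoint power confirms the working sample size. Power = Φ((0.10 − (p1 − p0))/SE − 1.645), with n = 36 per arm.
- 10% vs 5%: SE = √(0.1375/36) = 0.0618, and power = Φ(2.427 − 1.645) = 78.3% (exact enumeration 79.4%; stated 80%).
- 10% vs 10%: SE = √(0.18/36) = 0.0707, and power = Φ(1.414 − 1.645) = 40.9% (exact 41.7%; stated 41%).

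Both reproduce, and nothing below affects them.

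**2. Bias.** In 20,000 simulated trials with no arm effect (25% fair/poor at baseline, 30% at follow-up), the mean between-arm difference in raw status was 0.0 to 0.1 points. There is no bias.

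**3. Carry-over within an arm.** In that simulation 45%, 58% and 71% of follow-up fair/poor cases were already fair/poor at baseline, for binary correlations of 0.3, 0.5 and 0.7. With 40% at both times and latent correlation 0.5 to 0.8, the share is 60% to 75%.

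**4. Chance imbalance.** The SD of the baseline difference is √(2p(1 − p)/36). At p = 40% it is √(2 × 0.4 × 0.6/36) = 11.5 points. An imbalance of 15 points or more, in either direction, then occurs in about 19% of trials (exact 18.5%); the figure is 16% at p = 30% and 10% at p = 20%. This assumes simple randomisation. Balancing on immediate reconstruction (5.1) would lower it to the extent that reconstruction predicts the rating.

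With equal rates at both times, the expected carry-over is the imbalance times the binary correlation. Latent 0.5 to 0.8 corresponds to binary 0.33 to 0.59 at p = 40%, so 15 × 0.33 = 5 points and 15 × 0.59 = 9 points.

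**5. Precision.** At p = 40% the unadjusted 95% half-width is 1.96 × 11.5 = 22.6 points. A variance cut v multiplies it by √(1 − v) and is worth 36/(1 − v) women per arm.

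| Latent correlation | Variance cut v | Half-width (points) | Equivalent n per arm |
|---|---|---|---|
| none used | 0 | 22.6 | 36 |
| 0.2 | 2% | 22.4 | 37 |
| 0.3 | 5% | 22.0 | 38 |
| 0.5 | 14% | 21.0 | 42 |
| 0.8 | 39% | 17.7 | 59 |

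**6. Why not a simple change score.** With equal variance at both times, subtracting baseline multiplies the variance by 2(1 − r), where r is the binary correlation. At r = 0.33 this is 1.34, worse than ignoring baseline. It breaks even at r = 0.5 and is 0.82 at r = 0.59. Adjusting for the binary baseline gives 1 − r², that is 0.89 and 0.65.

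**7. Toxicity, sections side by side.** Section 10.1 ties a preexisting condition to worsening. Section 10.4 has the listed items graded at every evaluation. Sections 16.621 and 16.622 take the maximum grade by event type and are silent on baseline. The 10.1 rule can be read into them, but the text does not do so.

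**The case against.** The strongest reply is that 16.624 is descriptive. It specifies no test, its outcomes are secondary, and no decision rule depends on them. It also tabulates baseline beside 2 and 5 years by arm, so gross imbalance would be visible. BCTOS, which 11.3.2 names as the patient-rated cosmesis instrument, is already analysed as change in 16.623. All of this stands and limits the weight of the point. It does not supply the within-patient link for the Harvard-scale or panel ratings.

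The benefit could also be small. Section 7.54 allows an expander to be fully collapsed from simulation through radiotherapy, so baseline appearance may be temporary and weakly related to appearance at 2 years. That stands too, and is why the low-correlation rows are shown. The same feature calls for care in reading a table of worsening.

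Stronger readings are tempting, and the documents do not support them:
- A reader might infer that the arm comparison is biased, or that surgical results are presented as a radiotherapy effect. Randomisation removes the first, and nothing in the text labels the 2-year rate that way.
- A reader might infer that a baseline imbalance carries over in full. On the assumptions above, a third to three fifths of it does.
- A reader might infer that section 16.62 as a whole ignores baseline. Section 16.623 does not.
- A reader might infer that toxicity comparisons lose planned power. The plan specifies no test for those tables, and 10.1 already points to worsening, so only a reconciliation is needed.

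**Conclusion.** The point holds as one of efficiency and interpretation, not validity. Section 16.624 leaves the pre-radiotherapy rating unused within patient. The between-arm difference remains unbiased, but each arm's 2-year rate mixes surgical results with later change, and a sharper comparison is available from data already scheduled. The gain runs from negligible to material, depending on a correlation the documents do not give; both the carry-over and the variance figures also rest on an assumed 40% fair/poor rate. For toxicity, the supported conclusion is only that 16.621 and 16.622 should say how baseline grades are handled, consistent with 10.1. The primary endpoint, sample size and stated power are untouched.

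**What to change.** **16.624.** Keep the planned frequencies and confidence intervals. Add:
- the 2-year between-arm difference with its confidence interval, adjusted for the baseline rating by a proportional-odds model or as a standardised risk difference;
- a table of baseline category by 2-year category for each arm.

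Do not use a simple change score.

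**16.621 and 16.622.** Refer to the preexisting-condition rule in 10.1. State that a solicited 10.4 item counts as an adverse event when its grade is worse than that woman's baseline grade. Report the raw maximum grade as a supplement.

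**Cost.** A few sentences and minor extra analysis. No visit, rating or patient is added, because the baseline assessments are already in the test schedule.
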